3.1.2.4. Serious Adverse Events

SAEs follow standard definitions as outlined in Appendix 2 of the protocol. SAEs will be derived for the below intervals:

- From the time of consent through study completion.

PFIZER GENERAL BUSINESS

[figure not shown]

- From the time of vaccination through study completion.

3.2. Secondary Endpoints

Not applicable.

CCI

3.4. Baseline Variables

3.4.1. Baseline Definition

Day 1 is defined as the day of vaccination. Measurements or samples collected prior to vaccination on Day 1 are considered the baseline data for the assessments.

3.4.2. Demographics and Medical History

Demographic variables collected include sex, race, ethnicity, and date of birth. Age at the time of vaccination (in years) will be derived based on birthday. For example, if the vaccination date is 1 day before the participant's 19th birthday, the participant is 18 years old. For participants who were randomized but not vaccinated, the randomization date will be used in place of the date of vaccination for the age calculation. If the randomization date is also missing, then the date of the informed consent will be used for the age calculation.

Medical history of clinical significance will be collected and categorized according to the current version (at the time of reporting) of MedDRA.

3.4.3. E-Diary Transmission

[figure not shown]
An e-diary will be considered transmitted if any data for the local reactions or systemic events are present for any day. If all data are missing for all items on the e-diary for all 7 days after vaccination, then the e-diary will be considered not transmitted. An e-diary will be considered transmitted for a given day if any data are present for that day.

3.4.4. Nonstudy Vaccinations and Concomitant Medications

Receipt of the following concomitant medications and vaccinations will be recorded in the CRF:

- All nonstudy vaccinations received from 28 days prior to study enrollment through the conclusion of study participation.

PFIZER GENERAL BUSINESS

- The following medications, although prohibited as described in Section 6.8.1 of the protocol, will be collected from Visit 1 through the end of the study if required for medical care:
 - Immunosuppressant medications.
 - Monoclonal antibodies.
 - Systemic corticosteroids, ie, oral, IM, or IV. Topical, optic, otic, inhaled, intra-articular, or intrabursal corticosteroids will not be recorded or included.
 - Blood/plasma products or immunoglobulin.

Nonstudy vaccinations and concomitant medications will be categorized according to the latest version (at the time of reporting) of the WHO Drug Dictionary.

3.5. Safety Endpoints

3.5.1. Adverse Events

Local reactions, systemic events, AEs, and SAEs have been described above in the Primary Safety Endpoints section.

A 3-tier approach will be used to summarize AEs. Under this approach, AEs are classified into 1 of 3 tiers. Different analyses will be performed for different tiers.

[figure not shown]
- Tier 1 events: These are prespecified events of clinical importance and are maintained in a list in the product's safety review plan. As of the finalization of this SAP, no Tier 1 events have been identified for this vaccine.
- Tier 2 events: These are events that are not Tier 1 but are “common.” A MedDRA PT is defined as a Tier 2 event if its incidence is at least 1% in the pooled RSVpreF group or in the placebo group.
- Tier 3 events: These are events that are neither Tier 1 nor Tier 2 events.

3.5.2. Physical Examinations and Vital Signs

If the clinical assessment indicates that a physical examination is necessary to comprehensively evaluate the participant, a physical examination will be performed.

Physical examination findings collected during the study will be considered source data and will not be required to be reported, unless otherwise noted. Any untoward physical examination findings that are identified during the active collection period and meet the definition of an AE or SAE must be reported. Physical examination findings collected at Visit 1, if clinically significant, will be recorded on the medical history CRF.

PFIZER GENERAL BUSINESS

The participant's body temperature will be assessed prior to vaccination. It will only be used to assess any potential protocol deviation for vaccination temporary delay and will not be included as a baseline variable.

4. ANALYSIS SETS (POPULATIONS FOR ANALYSIS)

Data for all participants will be assessed to determine if participants meet the criteria for inclusion in each analysis population prior to unblinding and releasing the database and classifications will be documented per standard operating procedures.

Population	Description
Enrolled	All participants who sign the ICD.
Randomly assigned to study intervention	All participants who are assigned a randomization number in the IRT system.
Evaluable immunogenicity	All participants who meet the following criteria: 1. Are eligible for the study; 2. Receive the study intervention to which they were randomized at Visit 1; 3. Have a valid and determinate immunogenicity result from the blood sample collected within 27 to 42 days after vaccination; 4. Have no major protocol violations.
miITT	All randomized participants who receive study intervention and have at least 1 valid and determinate assay result after vaccination.
Safety	All randomized participants who receive study intervention.

Major protocol violations will be determined by clinical review. A major protocol violation is a protocol violation that, in the opinion of the sponsor's study medical monitor, would materially affect assessment of immunogenicity, eg, participant receipt of a prohibited vaccine or medication/treatment that might affect immune response or a medication error with suspected decrease in potency of the vaccine. The sponsor's medical monitor will identify those participants with protocol violations before any analysis is carried out.

[figure not shown]
5. GENERAL METHODOLOGY AND CONVENTIONS

5.1. Hypotheses and Decision Rules

5.1.1. Statistical Hypothesis

This study has 1 primary immunogenicity objective, which is to demonstrate that the immune responses for RSV A and RSV B induced by 3 lots of RSVpreF are equivalent. The objective will be evaluated at 1 month after vaccination for RSV A and RSV B using the evaluable immunogenicity population.

PFIZER GENERAL BUSINESS

The null hypothesis (H_0) for lot consistency for RSV A and RSV B is as follows:

$$H_0: |\ln(\mu_1) - \ln(\mu_2)| \geq \ln(1.5) \text{ or } |\ln(\mu_1) - \ln(\mu_3)| \geq \ln(1.5) \text{ or } |\ln(\mu_2) - \ln(\mu_3)| \geq \ln(1.5)$$

where $\ln(1.5)$ corresponds to a 1.5-fold equivalence margin, and $\ln(\mu_1)$, $\ln(\mu_2)$, and $\ln(\mu_3)$ are the natural log of the geometric mean of RSV antigen-specific NTs from participants receiving RSVpreF in Group 1, Group 2, and Group 3, respectively, measured 1 month after vaccination.

Lot consistency will be declared if the 2-sided 95% CI for the ratio of GMTs for every pair of RSVpreF lots is contained in the interval (0.667, 1.5), for both antigens simultaneously.

5.1.2. Multiplicity Adjustment

No multiplicity adjustment will be applied for this study. The primary objective of equivalence will be achieved only if the 1.5-fold equivalence criterion is met for every pair of between-lot comparisons from 3 lots and for both RSV A and RSV B antigens simultaneously. Each of the 6 statistical tests (3 pairwise comparisons between lots \times 2 RSV antigens) will use a 2-sided alpha level of 0.05.

5.2. General Methods

Unless stated otherwise, “vaccine group” in this section refers to participants receiving any 1 of the 3 RSVpreF lots or placebo. CIs for all endpoints in the statistical analysis will be presented as 2-sided at the 95% level unless specified otherwise.

For all the immunogenicity endpoints, the analysis will be based on the evaluable immunogenicity population. An additional analysis will be performed based on the mITT population if there is a large enough difference in sample size between the mITT population and the evaluable immunogenicity population. Participants will be summarized according to the vaccine group to which they were randomized.

The safety analyses will be based on the safety population. Participants will be summarized by vaccine group according to the study interventions they actually received.

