9.5. Sample Size Determination

Table 4 presents the power to demonstrate that the immune responses induced by 3 lots of RSVpreF are equivalent in regard to the 2 RSV antigens.

Pairwise lot-consistency comparisons will be based on the GMRs and the corresponding 95% CIs. For both antigens, it is assumed that true differences between lots are not larger than 0 (on the natural log scale). The SDs of the log titers for RSV A and RSV B are based on Study C3671001 data.

With 225 evaluable participants per vaccine group and the above assumptions, the power is 93.3% for declaring the overall equivalence of the 3 RSVpreF lots for both RSV A and RSV B.

Allowing for a nonevaluable rate of approximately 10%, up to 1000 participants will be enrolled in the study to provide the required sample size of approximately 900 participants for the evaluable population analysis. Participants who withdraw or are withdrawn from the study after randomization will not be replaced, regardless of the reason for withdrawal.

Table 4. Power for the Primary Immunogenicity Objective (Lot Consistency)

Endpoint	Within-Lot SD (Log Scale) ^a	Maximum Lot Difference (Log Scale)	Consistency Margin	Number of Evaluable Participants per Vaccine Group	Power to Declare Consistency ^b
RSV A	0.96	0	1.5-fold	225	98.5%
RSV B	1.07	0	1.5-fold	225	94.7%
Overall power to declare consistency for RSV A and RSV B simultaneously					93.3%

a. The reference study is C3671001.

b. The power to declare equivalence between all 3 pairwise comparisons assuming a mean difference of 0 between any 2 RSVpreF lots, at a 0.05 alpha level (2-sided).

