2.2. Study Design

This Phase 3, multicenter, parallel-group, placebo-controlled, randomized, double-blind study will be conducted in the US. Up to 1000 healthy women and men, 18 to \leq 49 years of age, will be enrolled. Allowing for a nonevaluable rate of approximately 10%, this will provide the required sample size of approximately 900 participants for the evaluable population analysis. Participants who withdraw or are withdrawn from the study after randomization will not be replaced, regardless of the reason for withdrawal.

There will be 4 study groups: Group 1, Group 2, Group 3 (representing 3 RSVpreF manufacturing lots), and placebo. Up to 1000 participants will be randomly assigned in a 1:1:1:1 ratio so that each group numbers approximately 250 participants.

There are 2 scheduled study visits. Participants will have blood samples for immunogenicity assessments collected both prior to vaccination (Visit 1) and 1 month after vaccination (Visit 2).

Local reactions (redness, swelling, and pain at the injection site) occurring at the RSVpreF or placebo injection site and systemic events (fever, fatigue, headache, vomiting, nausea, diarrhea, muscle pain, and joint pain) occurring within 7 days after vaccination will be prompted for and collected daily by the participant in an e-diary device or smartphone application.

AEs and SAEs will be collected from the signing of informed consent through Visit 2.

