6.1.1.1.2. Supplementary Analyses

The main analysis will also be performed based on the mITT population.

[figure not shown]

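### Could the mITT check on the lot-consistency result be dropped because its trigger is left undefined?

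*SAP*

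**What the plan says.** The primary analysis set is clear. SAP section 5.2 states: "For all the immunogenicity endpoints, the analysis will be based on the evaluable immunogenicity population". The same paragraph continues: "An additional analysis will be performed based on the mITT population if there is a large enough difference in sample size" between that population and the evaluable one. Protocol section 9.3.1 uses the same sentence. Neither document says how large is large enough, who judges it, or when.

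SAP section 6.1.1.1.2, which deals only with the primary immunogenicity endpoint, carries no condition: "The main analysis will also be performed based on the mITT population".

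SAP section 4 defines the mITT population as "All randomized participants who receive study intervention and have at least 1 valid and determinate assay result after vaccination". The evaluable population also requires eligibility, receipt of the randomized product, a blood draw 27 to 42 days after vaccination, and no major violation. On the last item, "Major protocol violations will be determined by clinical review". Membership of every population is to be settled "prior to unblinding and releasing the database and classifications will be documented per standard operating procedures".

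**The concern.** The single confirmatory claim rests on a per-protocol-type set that removes people for reasons arising after randomization, partly on the sponsor medical monitor's judgment. One of the SAP's own examples of a major violation is a dosing error thought to have weakened the vaccine, which is close to the question a lot-consistency trial asks. The mITT rerun is the only visible planned re-estimate of the lot ratios with those people put back.

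Section 5.2 covers every immunogenicity endpoint, so on its face it includes the primary one and makes that rerun depend on an open judgment. The trigger also looks like the wrong quantity. A difference in population size does not show whether exclusions were uneven between lots or linked to titer. If the condition governed, and the call were made after results were known, an unwelcome comparison could go unreported.

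**Working it through.** **1. The plan's own figures.** Protocol section 9.5 states: "Allowing for a nonevaluable rate of approximately 10%, up to 1000 participants will be enrolled in the study", for about 900 evaluable. SAP section 2.2 adds: "Up to 1000 participants will be randomly assigned in a 1:1:1:1 ratio so that each group numbers approximately 250 participants".

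- 900 / (1 − 0.10) = 1000, and 225 / (1 − 0.10) = 250. Both reproduce.
- Randomized minus evaluable is therefore about 25 per group, or 3 × 25 = 75 over the three lots. This is a ceiling on the planned mITT-evaluable gap, because anyone with no post-vaccination result is in neither set.

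**2. The texts side by side.**

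| Place | Covers | What it fixes |
|---|---|---|
| Protocol 9.3.1, SAP 5.2 | All immunogenicity endpoints | mITT run if the size gap is big enough; no cut-off |
| SAP 6.1.1.1.2 | Primary endpoint | mITT run, no condition |
| SAP 4 | Population membership | Settled before unblinding; violations identified before any analysis |
| SAP 6.5.2 | Exclusions | Summarized with reasons and listed; in-window and out-of-window draws tabulated by vaccine group |
| SAP 5.1.1, 6.1.1.1.1 | Declaration of consistency | Evaluable population only |

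A promise to run an analysis if the gap is big enough does not say that it will be withheld otherwise. Running it for the primary endpoint in all cases satisfies every row; omitting it breaches SAP 6.1.1.1.2. Protocol section 9 and SAP section 2 both allow the SAP to modify the protocol's plan, so the protocol sentence does not override the SAP's endpoint section.

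**3. Size of the effect.** Shift in a lot's mean log titer = (fraction excluded) × (mean of excluded − mean of the rest). Assume, as an illustration not taken from the documents, 235 mITT participants per lot, 10 excluded from one lot only, and a gap of 1.0. The Table 4 SDs are 0.96 and 1.07, so 1.0 is about one SD.

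- Shift = 10/235 × 1.0 = 0.043; exp(0.043) = 1.04.
- Against the margin: 0.043 / ln(1.5) = 0.043 / 0.405 = about 11%.
- The 10 people are 10/235 = 4.3% of that lot, but only 10/705 = 1.4% of the three lots.

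**4. When could that reverse a pass?** RSV B, SD 1.07, 225 evaluable per lot.

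- 95% CI half-width = 1.965 × 1.07 × √(2/225) = 0.198. The largest evaluable GMR that passes is exp(0.405 − 0.198) = 1.23.
- Put the 10 back in the higher lot, with titers higher by 1.0. The half-width becomes 1.965 × 1.07 × √(1/235 + 1/225) = 0.196. The mITT result fails only if the evaluable GMR exceeds exp(0.405 − 0.043 − 0.196) = 1.18.
- So a reversal needs an evaluable GMR between about 1.18 and 1.23. At 1.20, the evaluable upper limit is exp(0.182 + 0.198) = 1.46 and the mITT limit is exp(0.182 + 0.043 + 0.196) = 1.52.

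**5. The same question with equal exclusion fractions f in both lots.** The lot ratio needed among excluded participants is exp{[ln 1.5 − half-width(N) − (1 − f) ln g] / f}, with N = 225/(1 − f) and evaluable GMR g:

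| f | g = 1.10 | g = 1.20 |
|---|---|---|
| 2% | 327 | 4.6 |
| 5% | 11.4 | 2.2 |
| 10% | 3.7 | 1.7 |

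For small gaps, where a size condition would be most likely to suppress the run, only an extreme lot difference among the excluded would overturn a pass, unless the evaluable result was already near the limit.

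**The case for a change.** The strongest case is that sections 5.2 and 6.1.1.1.2 do not match within the SAP itself, so the clause letting the SAP modify the protocol does not settle the matter. A team that left the analysis out could cite section 5.2. Fixing membership before unblinding does not fix when the size gap is judged, or by whom. Step 4 also shows that a handful of exclusions, a small share of the total, can turn an upper limit of 1.46 into 1.52. Removing atypical responders can make lots look more alike, which in an equivalence trial is the direction to worry about.

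Much of this stands as description. The wording is inconsistent, the cut-off is undefined, and size is a poor trigger. What does not stand is the step to an analysis that may be dropped. Dropping it would contravene the section written for this endpoint. The gap is a count, which can be known blind once membership is settled, and the exclusions with their reasons are reported in any case.

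Deleting the condition outright would reach beyond the primary endpoint to any other immunogenicity endpoint, including those in redacted text, and would mean amending the protocol. Calling consistency robust only when both sets agree would add a rule the plan does not have. The stated estimand is hypothetical (SAP section 2.1.1.1), and the mITT set, analysed as randomized, does not target it. It can itself draw lots together if someone received another lot's product.

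**Conclusion.** No change is needed. The general section carries a vague default and the endpoint section carries a firm commitment. Following the plan as a whole already gives the six mITT ratios with their confidence intervals for RSV A and RSV B. The declaration of lot consistency, its type I error and the sample size are the same under either reading, because they use the evaluable population only. Under the illustrative assumptions the possible shift is about 1.04-fold, and it could matter only for an evaluable RSV B ratio between about 1.18 and 1.23.

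This rests on two things: treating the endpoint-specific section as controlling, which is the natural reading, and taking the population decisions to be made before unblinding as SAP section 4 requires. A cross-reference in section 5.2 would tidy the text if the SAP were reopened for another reason, but it would not change what is run or concluded.

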5.2.1. Analyses for Binary Data

Descriptive statistics for categorical variables (eg, proportions) are the percentage (%), the numerator (n) and the denominator (N) used in the percentage calculation, and the 95% CIs where applicable.

The exact 95% CI for binary endpoints for each group will be computed using the F distribution (Clopper-Pearson method).¹ The 95% CI for the between-group difference for binary endpoints will be calculated using the Miettinen and Nurminen method.²

The 3-tier approach will be used to summarize AEs. For both Tier 1 (if any are identified during the study) and Tier 2 events, a 95% CI for the between-group difference in proportions will be calculated based on the Miettinen and Nurminen method.² In addition, for Tier 1 events (if any), the asymptotic p-values will also be presented for the difference in proportions, based on the same test statistic and under the assumption that the test statistic is asymptotically normally distributed. For Tier 3 events, counts and percentages for each vaccine group and the pooled RSVpreF lots will be provided.

5.2.2. Analyses for Continuous Data

[figure not shown]
Unless otherwise specified, descriptive statistics for continuous variables are n, mean, median, standard deviation, minimum, and maximum.

The CI for the mean of the continuous variable will be constructed by the standard method based on Student's t distribution.

5.2.2.1. Geometric Means

Continuous immunogenicity endpoints will be logarithmically transformed for analysis. Geometric means and associated 2-sided 95% CIs will be derived by calculating group means and CIs on the natural log scale based on the t distribution, and then exponentiating the results.

[figure not shown]
CCI

5.2.2.3. Geometric Mean Ratios

The GMRs will be calculated as the mean of the difference of logarithmically transformed assay results between 2 RSVpreF lots and exponentiating the mean. Two-sided CIs will be obtained by calculating CIs using Student's t distribution for the mean difference of the logarithmically transformed assay results and exponentiating the confidence limits.

CCI

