2. INTRODUCTION

Pfizer is currently developing a vaccine, RSVpreF, for the prevention of RSV-associated LRTI, protecting infants by maternal immunization during pregnancy and protecting adults 60 years of age and older via direct immunization.

RSV is the leading cause of bronchiolitis and viral pneumonia in infants and can lead to fatal respiratory distress, especially in those with risk factors, including premature infants with underlying cardiopulmonary disease, or in the absence of effective healthcare systems.¹ However, most cases of RSV disease occur in healthy, full-term infants without risk factors.² Worldwide, RSV kills approximately 118,200 children annually, with about half of those deaths occurring in infants under 6 months of age, and the majority of those occurring in resource-limited countries.^{3,4} In the US, RSV is the leading cause of infant hospitalization, with more than 60,000 hospitalizations of children 12 months of age and younger annually.^{5,6} There is increasing evidence that the link between severe RSV disease in infancy and wheezing later in childhood may be causal.^{7,8} Like influenza, RSV infection follows a seasonal pattern, causing illness primarily in the cooler months of the year in temperate regions and during the wet season in tropical countries with seasonal rainfall.⁹ Infection is essentially universal by the time children reach 2 years of age.¹⁰

No specific treatments for RSV exist, and available prophylactic measures (ie, RSV monoclonal antibody) are limited to use in only those infants at highest risk; additionally, in LMICs, use of available RSV prophylaxis is cost-prohibitive.^{11,12} While active immunization against RSV in infants might be an option, multiple efforts extending over half a century to develop a safe and effective RSV vaccine to protect infants from disease have yielded little success. The early peak of disease presents a further obstacle to an active vaccination strategy for infants. Given these challenges, maternal immunization to protect infants early in life offers an attractive strategy for infant disease prevention.

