8.1.2. Immunogenicity Assessments

8.1.2.1. Blood Collection

Blood samples for immunogenicity assessments will be collected from all enrolled participants prior to study vaccination at Visit 1 (approximately 20 mL per sample) and at Visit 2 (1 month after Visit 1) (approximately 80 mL per sample).

Instructions for the collection and handling of biological samples will be provided in the laboratory manual. The actual date and time of each sample will be recorded.

The immunogenicity samples must be processed and shipped as indicated in the instructions provided to the investigator site to maintain sample integrity. Any deviations from the immunogenicity sample-handling procedure (eg, sample collection and processing steps, interim storage, or shipping conditions), including any actions taken, must be documented, and reported to the sponsor. On a case-by-case basis, the sponsor may make a determination as to whether sample integrity has been compromised.

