9.3.1.2.1. Geometric Mean Ratios

[figure not shown]
The GMRs will be calculated as the mean of the difference of logarithmically transformed assay results between 2 vaccine groups and exponentiating the mean. Two-sided CIs will be obtained by calculating CIs using Student’s t-distribution for the mean difference of the logarithmically transformed assay results and exponentiating the confidence limits.

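### The primary GMR analysis leaves out the baseline RSV titer that the trial already collects, so the lot-equivalence confidence intervals are wider than they need be if baseline and 1-month titers correlate

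*SAP*

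**What the plan says.** SAP 6.1.1.1.1 (Main Analysis) refers to SAP 5.2.2.3 for its method: "The GMRs will be calculated as the mean of the difference of logarithmically transformed assay results between 2 RSVpreF lots and exponentiating the mean". The CI comes from Student's t distribution on the log scale. Protocol 9.3.1.2.1 matches: "The GMRs will be calculated as the mean of the difference of logarithmically transformed assay results between 2 vaccine groups and exponentiating the mean". Neither names a covariate.

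The visible supplementary analysis of the primary immunogenicity endpoint changes only the population: "The main analysis will also be performed based on the mITT population". SAP 6.4 adds an optional subgroup analysis by sex.

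The baseline sample is already in the design. Protocol 8.1.2.1: "Blood samples for immunogenicity assessments will be collected from all enrolled participants prior to study vaccination at Visit 1". SAP 3.4.1: "Measurements or samples collected prior to vaccination on Day 1 are considered the baseline data for the assessments". SAP 5.3.2 gives a rule for fold rises when a titer is below the LLOQ, which presupposes a baseline titer.

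The decision rule (Protocol 9.1.2, SAP 5.1.1) requires the 95% CI of every pairwise GMR, for both antigens, to lie within (0.667, 1.5).

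**The concern.** In a randomized comparison of mean log titers, adjusting for a baseline value that predicts the outcome removes the variance it explains and leaves the target ratio unchanged. Adults bring prior RSV exposure to this trial; Protocol 2 says "Infection is essentially universal by the time children reach 2 years of age". A correlation between pre- and post-vaccination titers is therefore plausible, although this says nothing about its size.

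One CI that is too wide, for one pair and one antigen, fails the whole objective. Withdrawn participants are not replaced and there is a single final analysis. With the margin and sample size fixed, residual SD is the quantity left that can narrow the CIs. What is at stake is precision and the chance of a false failure. Bias and type I error are not in question.

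**Working it through.** **Inputs.** Protocol 9.5, Table 4: SD of ln titer 0.96 (RSV A) and 1.07 (RSV B), 225 evaluable per lot, true lot difference 0. Protocol 9.1.2 and 9.1.3: margin ln(1.5) = 0.4055, two-sided 95% CIs, all three pairs and both antigens must pass. The documents give no r, so it is an assumption, shown from 0 to 0.6.

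**The plan's own figure.** Protocol 9.5 says: "With 225 evaluable participants per vaccine group and the above assumptions, the power is 93.3" per cent. That is the product of the two antigen powers, 0.985 × 0.947 = 0.933. Simulating the documented 95% CI rule (1,000,000 runs per antigen) gives 96.8% for RSV A, 90.0% for RSV B and 87.1% overall, so the stated figure does not reproduce. It does agree with 90% CIs and a Bonferroni bound over the three pairs (98.6%, 94.7%, 93.4% overall). That discrepancy is a separate matter. The starting point here is the power under the rule as written.

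**Effect of adjustment.** Residual SD = SD × √(1 − r²), and CI width on the log scale shrinks by the same factor. At r = 0.5, √(1 − 0.25) = 0.866; simulated least-squares fits gave a standard-error ratio of 0.866.

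| Assumed r | CI narrower by | Overall power |
|---|---|---|
| 0 | 0% | 87.1% |
| 0.1 | 0.5% | 87.7% |
| 0.2 | 2.0% | 89.4% |
| 0.3 | 4.6% | 92.0% |
| 0.35 | 6.3% | 93.4% |
| 0.4 | 8.3% | 94.9% |
| 0.5 | 13.4% | 97.6% |
| 0.6 | 20.0% | 99.3% |

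By antigen (RSV A / RSV B), power is 96.8% / 90.0% at r = 0, 98.7% / 94.7% at r = 0.35 and 99.6% / 97.9% at r = 0.5.

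**Largest observed RSV B ratio that still passes.** This is exp(ln 1.5 − h), where h = t × 1.07 × √(1 − r²) × √(2/225) and t = 1.965.
- r = 0: h = 0.1983, limit 1.230
- r = 0.2: h = 0.1943, limit 1.235
- r = 0.35: h = 0.1857, limit 1.246
- r = 0.5: h = 0.1717, limit 1.263

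**If lots differ slightly.** With an assumed largest true ratio of 1.1, overall power is 71.3% at r = 0, 78.4% at r = 0.3 and 89.2% at r = 0.5.

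**Cost when baseline is uninformative.** Participant-level simulation with a fitted slope (20,000 runs, error about ±0.3 points) at r = 0: 87.1% adjusted, 87.2% unadjusted.

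**Type I error.** RSV B, two lots exactly 1.5-fold apart, r = 0.5 (40,000 runs): 2.1% unadjusted, 2.3% adjusted, both under 2.5%.

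**Missing baselines.** Setting 0%, 2% or 5% of baselines to the overall mean gives 93.3%, 93.3% and 92.9% at r = 0.35, and 97.8%, 97.6% and 97.1% at r = 0.5.

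**Correlation between antigens.** The overall figures treat RSV A and RSV B as independent, as Table 4 does. With an assumed correlation of 0.5, 0.7 or 0.9, the gain at r = 0.35 falls from about 6.3 points to roughly 6.0, 5.5 and 4.9.

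**The case against.** The strongest reply is that nothing is broken. The unadjusted interval estimates the prespecified ratio, and in an equivalence test a wide interval only makes success harder, so the sponsor alone bears the risk. At an observed GMR of 1 the expected RSV B interval is 0.820 to 1.219, comfortably inside the limits. The payoff depends on an r that the documents do not give, and at r = 0.2 or less it is at most about 2 points of power. The primary analysis would have to be amended again, after the sample size and threshold were already changed following regulator feedback (SAP Table 1). Redacted text could also hold an adjusted analysis.

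Much of this stands. It is a matter of efficiency, the gain could be small, and the amendment is not trivial. Age and sex are also collected, so baseline titer is not the only available covariate. Because the assay text in Protocol 8.1.2.2 is partly redacted, neutralization testing of the Visit 1 sample is inferred from the blood-collection, baseline and fold-rise text. A redacted analysis cannot be judged.

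None of it removes the point. The main-analysis text is visible and refers only to the unadjusted method. Adjustment costs essentially nothing at r = 0. The sponsor can also find out r before amending: the planning SDs come from C3671001, and Protocol 2.2.1 reports fold rises from before vaccination to 1 month in that study, so paired titers exist.

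**Conclusion.** The concern holds as a precision point. The primary analysis is valid but leaves unused a covariate already in the design, so its CIs are wider than necessary to the extent that r exceeds zero. The benefit is small at r of 0.3 or less (CIs under 5% narrower) and material at r of 0.5 or more (at least 13% narrower, overall power about 97.6% against 87.1%). Under the 95% CI rule, r of about 0.35 would bring power to the stated 93.3%.

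These figures assume 225 evaluable per lot, the Table 4 SDs, zero true lot difference and independence between antigens. Correlated antigens shrink the gain somewhat; a small true lot difference enlarges it. The change is worth making, though how much it yields is uncertain until r is known.

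**What to change.** Before unblinding, estimate r from the paired titers in C3671001, then amend SAP 5.2.2.3 and 6.1.1.1.1 and Protocol 9.3.1.2.1 and 9.3.2 as follows.

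- **Model.** For each antigen, fit one linear model of ln(1-month titer) on lot (Groups 1 to 3) and ln(baseline titer of the same RSV subgroup). Exponentiate the adjusted pairwise differences and their 95% CIs.
- **Decision rule.** Keep (0.667, 1.5) for all six comparisons.
- **Supplementary analysis.** Retain the unadjusted GMR.
- **Baselines below the LLOQ.** Use the existing 0.5 × LLOQ rule in SAP 5.3.2.
- **Missing baselines.** The assay criterion for the evaluable set covers only the post-vaccination sample: "Have a valid and determinate immunogenicity result from the blood sample collected within 27 to 42 days after vaccination". Prespecify a rule so that no one is dropped for lack of a baseline, for example one overall mean value for the covariate. State it as an exception to the no-imputation text in Protocol 9.1.1 and SAP 5.3.2, which would still govern the 1-month outcome.

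This needs no new samples or participants. Because it changes the primary analysis, it needs a formal protocol amendment (Protocol 9, SAP 2) with IRB/EC approval and, if the amendment is substantial, health authority approval (Protocol 10.1.1), together with a SAP revision.
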